7.2 Safety Definitions

Adverse Event

An adverse event (AE) is any untoward or undesirable medical occurrence in a subject receiving treatment according to the protocol. This includes occurrences which are not necessarily caused by or related to administration of the research procedures. An adverse event can therefore be any

unfavourable and unintended sign, symptom or disease temporally associated with the use of the intervention or research procedures whether or not considered to be related to the intervention/research procedures.

Adverse events that might be expected to occur at a higher rate in this group of participants include episodes of self-harm not requiring hospital admission and worsening of depression sufficient to require referral to a clinician. Although these AEs are expected, they will still be reported as data in this study. Variations in mood, including worsening of depression that does not lead to self-harm or hospitalisation, are commonly seen during therapy and would not be reported as individual adverse events. Expected events are listed in full in section 7.9.

There may be more AE reports in the intervention group as a result of their regular contact with the study team (i.e. receipt of up to 18 EMDR sessions with the study therapist, and more regular completion of the PHQ-9 and related participant safety risk assessments as part of therapy). This will be taken into consideration when interpreting the pattern of AEs.

Adverse Reaction

An adverse reaction (AR) is any undesirable experience that has happened to a subject that is suspected to be caused by the intervention.

Serious Adverse Event

A serious adverse event (SAE) is any adverse event which:

- results in death,
- is / was life threatening*,
- requires hospitalisation or prolongs an ongoing hospitalisation**,
- results in persistent or significant disability or incapacity,
- consists of a congenital anomaly or birth defect,

Other important medical events that may jeopardise the subject and may require medical or surgical intervention to prevent one of the outcomes listed above should also be classed as an SAE.

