There may be more SAE reports in the intervention group as a result of their regular contact with the study team (i.e. receipt of up to 18 EMDR sessions with the study therapist, and more regular completion of the PHQ-9 and related participant safety risk assessments as part of therapy). This will be taken into consideration when interpreting the pattern of SAEs.

Suspected Serious Adverse Reaction (SSAR)

A suspected serious adverse reaction (SSAR) is any serious adverse event that is suspected (possibly or probably or definitely) to be related to the intervention.

^{*&}quot;Life-threatening" in the definition of "serious" refers to an event in which the participant was at risk of death at the time of the event; it does not refer to an event which hypothetically might have caused death if it were more severe.

^{** &}quot;Hospitalisation" is defined as an unplanned overnight stay. Note, however, that the patient must be formally admitted — waiting in outpatients or an Emergency Department would not count as hospitalisation (even though this can sometimes be overnight). Planned hospital stays would not be counted as SAEs, nor would time in hospital for "social reasons" (e.g. respite care, the fact that there is no-one at home to care for the patient). Also, if patients had a day-case operation, this would not qualify as hospitalisation. However, if a planned operation was brought forward because of worsening symptoms, this would be considered as an SAE. Hospitalisations for the purpose of the intervention are an exception to SAE reporting unless complications occur.

Non-IMP Suspected Unexpected Serious Adverse Reaction (Non-IMP SUSAR)

An SAE that occurs in a non-IMP trial and is:

- "Related" that has, possibly, probably or definitely resulted from administration of any of the research procedures, and
- "Unexpected" that is, the type of event is not listed in the protocol (or above) as an expected occurrence.

All AEs will be assessed for seriousness, causality (relatedness) and expectedness by a clinical PI or nominated deputy clinician. The clinical PI at each centre will also record whether an event is considered to be related to the participant's mental health. We will develop a detailed, study-specific standard operating procedure for reporting and recording adverse events in line with the Sponsor's requirements. This will be in place prior to the commencement of recruitment activities.

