7.7 Identification of AEs

[figure not shown]
AEs are expected to occur throughout the course of the trial. Local researchers are responsible for recording AEs for their participants during the trial.

We anticipate that some AEs may be identified during EMDR appointments for participants allocated to the intervention. Up until the 52 week follow up, AEs may also be detected via researcher contact to encourage questionnaire completion, or via completion of study questionnaires (across both UC and EMDR groups). We will not actively monitor for events outside of study questionnaires. However, the central and/or local research team will report any AEs that occur should they become aware, as below.

[figure not shown]
We anticipate that most AEs will be identified via study questionnaires. For example, participants will be asked about suicidal thoughts as part of the PHQ-9 and BDI-II questionnaires, and about hospital treatment as part of the 26 week and 52 week questionnaires; their responses and other disclosures may lead to further investigation in relation to AE reporting. The central and/or local team will communicate with clinical PI and GP practices if additional information is required, e.g., to ascertain the nature and severity of an AE. If the study team become aware of an AE, they will assess and log this according to trial recording and reporting procedures; see below.

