7.9 Expected events

Expected events are clinical outcomes that routinely occur when delivering the intervention.

Expected AEs and SAEs that are a more common occurrence in this study population regardless of the study are listed below. Although these events are expected, they will still be reported in this study.

- Self-harm
- Self-harm leading to hospitalisation
- Suicide attempts
- Suicide attempts leading to hospitalisation
- Worsening of depression which requires referral to a clinician
- Worsening of depression leading to hospitalisation

All AEs will be assessed for seriousness, severity, causality and expectedness by a clinical PI or nominated deputy clinician. Relatedness to mental health will also be assessed. We will develop a detailed, study-specific standard operating procedure for reporting and recording adverse events in line with the Sponsor's requirements. This will be in place prior to the commencement of recruitment activities.

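### Protocol section 7.2 both requires and waives adverse event reporting for worsening depression that needs referral to a clinician; section 7.9 requires it

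*Protocol*

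**What the plan says.** Three statements in the Protocol bear on the same kind of event.

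- **Section 7.2, expected AEs.** Among the AEs anticipated at a higher rate in this population is "worsening of depression sufficient to require referral to a clinician. Although these AEs are expected, they will still be reported as data in this study".
- **Section 7.2, the sentence that follows.** Its subject is variation in mood, and it includes within that "worsening of depression that does not lead to self-harm or hospitalisation, are commonly seen during therapy and would not be reported" as individual adverse events. The section then refers the reader onward: "Expected events are listed in full in section 7.9".
- **Section 7.9.** The list contains "Worsening of depression which requires referral to a clinician" and, as a separate entry, "Worsening of depression leading to hospitalisation". Of the listed items it says: "Although these events are expected, they will still be reported in this study".

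Two further provisions matter for how the rule would be applied. Section 7.7 says "Local researchers are responsible for recording AEs for their participants during the trial", and section 7.10 has the clinical PI check the individual reports. The footnote to the serious adverse event definition in 7.2 counts only formal overnight admission as hospitalisation: "waiting in outpatients or an Emergency Department would not count as hospitalisation".

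**The concern.** The reporting rule and the exemption use different thresholds. The rule starts at referral to a clinician. The exemption stops only at self-harm or hospitalisation. Events between those two points are covered by both.

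Worsening of the condition under treatment is a central harm in a depression trial. The first decision on whether to record such an event lies with local researchers. An event set aside under the exempting sentence produces no AE report, so there is nothing for the clinical PI to check under 7.10. With three centres, practice could differ between researchers and sites, and the harms table would then reflect which sentence people followed. The exempting sentence also speaks of what is usual during therapy, so staff might apply it more readily in the EMDR arm. That is a risk of the wording; the protocol does not state it as a rule.

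**Working it through.** The plan states no figure on this point, so there is none to reproduce. The check is to take each level of worsening through the three statements.

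| Event | 7.2, expected AEs | 7.2, exemption | 7.9 list | Result |
|---|---|---|---|---|
| Worsening below referral level, no self-harm, no admission | Not named | Not reported individually | Not listed | Consistent |
| Worsening needing referral, no self-harm, no admission | Reported | Not reported individually | Reported | **Conflict** |
| Worsening with self-harm | Self-harm reported | Outside exemption | Self-harm reported | Consistent |
| Worsening with admission | Not named here | Outside exemption | Reported | Consistent |

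Only the second row conflicts. Section 7.9 gives admission its own entry, so the referral entry must cover people who were not admitted, and those are the people the exemption removes.

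**Share of the list affected.** The six entries in 7.9 are self-harm; self-harm with hospitalisation; suicide attempt; suicide attempt with hospitalisation; worsening needing referral; and worsening with hospitalisation. The exemption conflicts with one of the six, and with one of the two that concern worsening of depression.

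**Possible number of participants.** The documents give no rate for referral-level worsening. For an assumed share *p* of the 380 participants, the number with at least one such event is *p* × 380:

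- 1%: 0.01 × 380 = 3.8, about 4
- 5%: 0.05 × 380 = 19
- 10%: 0.10 × 380 = 38

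These are illustrations only; the contradiction does not depend on them.

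**A conditional extension.** If the hospitalisation footnote in 7.2 also governs the exempting sentence, worsening that leads to an Emergency Department attendance without formal admission falls within the exemption too. Section 7.2's clause on other important medical events may bring some of these cases back in as serious events.

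**The case against.** The best defence is that the exempting sentence is about ordinary mood fluctuation. Its subject is variation in mood, and it comes straight after a statement that referral-level worsening is reported. Taking the specific rule first and the general one as the remainder gives a single workable instruction. That is probably what was meant, but the text does not say it: the sentence gives its own cut-off and makes no exception for referral.

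A second defence is that the verbs differ. Referral-level worsening is reported as data, while the exemption is only from individual AE reports, so aggregate counts might satisfy both. This does not hold up. Section 7.2 calls these events AEs, and both 7.2 and 7.9 say that all AEs are assessed for seriousness, causality and expectedness by a clinical PI or deputy. That is individual handling.

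A third is that the operating rule lies elsewhere. The content of the 7.8 overviews could not be read in the text available for this review, and the study-specific AE procedure is still to be written. Either may state the rule correctly, and staff may work from those. This stands as a limit on the practical consequence, but it would not make the sentence in 7.2 correct.

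Finally, the events would not vanish. Sections 7.1 and 7.7 give routes by which safety concerns and questionnaire responses can reach the clinical PI. PHQ-9 is collected at every follow-up, and BDI-II at 26 and 52 weeks, in both arms. This also stands: the clinician may hear of the event and the symptom scores are kept. None of these routes guarantees an AE record, however.

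**Conclusion.** The contradiction holds on the wording alone and needs no outside source. For worsening that requires clinician referral without self-harm or admission, two statements say report and one says do not report individually. If followed, the exempting sentence drops a harm that the protocol elsewhere undertakes to report.

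The size is small. One of six listed event types is affected. Worsening with self-harm or admission is reportable under every statement. No efficacy outcome or analysis changes. How many participants would be involved is unknown, and the counts of 4, 19 and 38 rest wholly on assumed rates. Whether events would actually be lost depends on what the 7.8 overviews and the AE procedure say. It is a minor inconsistency, but a clear one.

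**What to change.** In section 7.2, add referral to a clinician to the exemption's cut-off, so that it covers only worsening that leads to none of three things: referral to a clinician, self-harm or hospitalisation. State that the rule applies equally in both arms. Check that the 7.8 overviews agree, and write the AE procedure to match 7.9.

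The cost is a few words in one sentence plus that check. No new data are needed, and the design and analysis are unchanged. The one drawback is somewhat more non-serious AE forms if staff have been following the exempting sentence.

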7.3 Classification of severity (intensity)

Mild event:	An event that is easily tolerated by the participant, causing minimal discomfort a
	not interfering with everyday activities.
Moderate event	An event that is sufficiently discomforting to interfere with normal everyday
	activities.
Severe event:	An event that prevents normal everyday activities.

7.4 Classification of relatedness (causality)

Not related	Temporal relationship of the onset of the event, relative to administration of the intervention, is not reasonable or another cause can by itself explain the occurrence of the event.					
Unlikely to be related Temporal relationship of the onset of the event, relative to administration intervention, is unlikely and it is likely there is another cause which can leave explain the occurrence of the event.						
Possibly related	Temporal relationship of the onset of the event, relative to administration of the intervention, is reasonable but the event could have been due to another, equally likely cause.					
Probably related	Temporal relationship of the onset of the event, relative to administration of the intervention, is reasonable and the event is more likely explained by the intervention than any other cause.					
Definitely related	Temporal relationship of the onset of the event, relative to administration of the intervention, is reasonable and there is no other cause to explain the event, or a rechallenge (if feasible) is positive.					

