As part of the baseline appointment, those who are eligible will be asked about adverse childhood experiences (using the childhood trauma questionnaire (CTQ) [55]) and stressful or traumatic events in adulthood (using a measure of stressful life events taken from the Adult Psychiatric Morbidity surveys [56] which has been widely used in previous depression trials [9], and the Life Events Checklist (LEC-5) that asks about traumatic events [57]).

Patients will be asked to describe (in a few words) the experience that they associate most strongly with their depression and asked to rate the vividness and emotional intensity of the memory associated with that event (using a visual analogue scale (VAS) (0-10)). Patients will only be asked to provide enough detail about the experience so that they know which experience they should be thinking about when asked to re-rate these questions as part of the follow-up questionnaires. They will not need to discuss the event in detail. Symptoms of re-living, avoidance and hyper-arousal related to that experience will be measured using the International Trauma Questionnaire (ITQ) [58]. In addition, the number and strength of negative self-beliefs will be recorded using a list adapted from an existing checklist [19].

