7.6 Safety reporting period

Adverse events/reactions will be recorded and reported from the point of consent (baseline assessment) until the 12-month follow-up assessment or point of withdrawal from the study.

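### The causality scale in 7.4 rates events against EMDR alone, while 7.2 defines a SUSAR by relation to any research procedure, so harm provoked by the assessments has no grade that records it as related

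*Protocol*

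**What the plan says.** Protocol 7.2 (Safety Definitions) uses two reference exposures. The adverse event definition covers events associated in time with either the intervention or the research procedures. The non-IMP SUSAR definition calls an SAE related if it "possibly, probably or definitely resulted from administration of any of the research procedures", and unexpected if "the type of event is not listed in the protocol (or above) as an expected occurrence". The adverse reaction and SSAR definitions are narrower. An SSAR is "any serious adverse event that is suspected (possibly or probably or definitely) to be related to the intervention".

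Protocol 7.4 (Classification of relatedness) has five grades. All judge the timing of onset against the intervention. *Not related* applies where the "Temporal relationship of the onset of the event, relative to administration of the intervention, is not reasonable", and equally where the timing "is not reasonable or another cause can by itself explain the occurrence of the event". *Probably related* requires that "the event is more likely explained by the intervention than any other cause". No grade mentions research procedures.

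Protocol 7.6 has events recorded "from the point of consent (baseline assessment) until the 12-month follow-up assessment". Under 6.5, randomisation follows completion of the baseline assessments. Under 7.7, events may be picked up through study questionnaires in both arms, and 7.2 and 7.9 require every adverse event to be assessed for causality.

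At baseline (6.3.3), eligible participants complete the CTQ, LEC-5 and ITQ, name the experience they link most strongly to their depression, and are "asked to rate the vividness and emotional intensity of the memory associated with that event". Table 2 repeats the memory ratings, a shortened ITQ and the self-belief items at five of the follow-ups.

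**The concern.** The SUSAR definition borrows the terms possible, probable and definite from the causality scale, but the scale defines those terms for a different exposure. A clinical PI who follows 7.4 answers whether EMDR caused the event. The SUSAR definition asks whether anything done for the research caused it.

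The gap matters here because the trial's research procedures include prompted recall of distressing experiences, asked of both arms and first asked before allocation. Distress after such an assessment is a foreseeable procedure-related harm, and 7.2 is worded to include it. At stake are whether an unexpected serious event of this kind is classified as a SUSAR, and whether the relatedness codes seen by the DMC can show procedure-related harm at all.

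**Working it through.** The plan gives no figure on this point and no arithmetic applies. The check is to set the definitions side by side and apply them to each situation that can arise.

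**Reference exposure in each definition**

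| Item | Section | Relatedness judged against |
|---|---|---|
| Adverse event (scope) | 7.2 | Intervention or research procedures |
| Adverse reaction | 7.2 | Intervention |
| SSAR | 7.2 | Intervention |
| Non-IMP SUSAR | 7.2 | Any research procedure |
| Causality grades (all five) | 7.4 | Intervention |

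The adverse event definition names the intervention and the research procedures separately. The word intervention in 7.4 therefore cannot easily be read as already including the questionnaires.

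**Applying 7.4 literally to an event provoked by an assessment**

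1. *Between consent and randomisation.* Reporting is open (7.6) and the trauma and memory questions are asked (6.3.3). No EMDR has been given, so timing relative to EMDR cannot be reasonable. The possible, probable and definite grades all require reasonable timing, so none is available. The grade is *Not related*.
2. *Usual-care arm, any time to 52 weeks.* Trial EMDR is never given. The result is the same as in step 1.
3. *EMDR arm, before the first session.* The result is again the same. Section 6.6.1 gives a mean of 3 weeks to start therapy in previous trials.
4. *EMDR arm, during or after therapy.* Timing relative to EMDR may be reasonable. But a questionnaire that can by itself explain the event is another cause, and the second limb of *Not related* then applies. If the two explanations are equally likely, *Possibly related* is available, but it records a possible link to EMDR and not to the assessment.

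In steps 1 to 3, a rater who preferred *Unlikely to be related* would still fall short of the possible, probable or definite grades that the SUSAR definition needs.

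**Applying 7.2 to the same events**

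If the assessment possibly, probably or definitely caused an SAE, it is related. If its type is not on the expected list in 7.9, it is a SUSAR. The related limb cannot be met through 7.4 in steps 1 to 3, and in step 4 only by way of a suspected link to EMDR. The two sections give different answers for the same event.

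**What does not change**

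- Section 7.10 requires all SAEs to reach the sponsor within 24 hours, whatever the causality grade.
- The DMC reviews overall safety data (7.10).
- Self-harm, suicide attempts and worsening depression, with or without hospitalisation as listed in 7.9, are expected. They fail the unexpected limb under either causality grade.

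**The case against.** The strongest reply is that this is only a wording mismatch. SAEs are reported whatever their grade. The clinical PI assigns causality by medical judgement (7.10) and separately records whether the event relates to mental health. A study-specific adverse event SOP is promised before recruitment (7.2, 7.9) and is not shown, and the flow charts under 7.8 did not survive text extraction. Either could put a wider relatedness question to the PI. Section 7.4 also agrees with the adverse reaction and SSAR definitions, which concern the intervention by design.

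Most of this stands as a limit on the consequences. It does not remove the conflict. Judgement needs a category in which to be recorded, and three centres could resolve the conflict in different ways. An SOP should apply the protocol's definitions, not choose between two that disagree. The agreement with the SSAR definition is a good reason to leave that definition alone.

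A reader might infer three stronger things that the protocol does not support:

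- *That a usual-care participant admitted after self-harm following the questionnaires would be a missed SUSAR.* Self-harm leading to hospitalisation is listed as expected in 7.9, so it could not be a SUSAR under either grade.
- *That assessment harm in the EMDR arm would be counted as therapy harm.* The alternative-cause limb of 7.4 pushes it mainly towards *Not related*. The protocol also plans no formal between-arm comparison of related events: section 10 has none, and 7.2 speaks only of interpreting the pattern of events.
- *That the size of the usual-care arm measures the problem.* It counts people for whom the related grades are unavailable, not events that would be misclassified.

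**Conclusion.** The concern holds as an internal contradiction in the safety section. Taken literally, 7.4 cannot record relatedness to a research procedure, while the SUSAR definition in 7.2 depends on it. There are two consequences. An SAE of an unlisted type that was caused by a research procedure would miss SUSAR classification, and the relatedness coding of other adverse events would miss procedure-related harm in both arms.

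The effect is confined to classification. Event capture, 24-hour SAE reporting, the efficacy analysis and the sample size are unaffected. The number of affected events cannot be estimated, because the protocol gives no rate of procedure-related harm.

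The conclusion assumes that 7.4 is applied as written and that the unseen SOP and reporting flow charts do not widen it. The mismatch between the sections is certain from the text. How often it would matter in practice is not. A correction is worth making because the rule gives the wrong answer as written and costs almost nothing to repair.

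**What to change.** Reconcile 7.4 with 7.2. Reword each of the five grades so that timing and cause are judged against the intervention or any research procedure. Add one field to the adverse event form to record which of the two, EMDR or a research procedure, the event is judged related to. With that field, the adverse reaction and SSAR definitions can stay specific to the intervention, and the SUSAR definition can be applied as it stands. Carry the same wording into the adverse event SOP.

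The cost is a wording change in 7.4 and one form field. No visits, staff or changes to participant procedures are needed.
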